Design: To address the impact of a popular, over-the-counter gel lubricant use in MSM on PrEP, investigators at Emory University will collaborate with the Centers for Disease Control and Prevention (CDC) to conduct a randomized clinical trial of 90 MSM. Men will be randomized into a 3-arm study as follows: (1) daily oral Truvada® only, (2) daily gel lubricant applied rectally only or (3) oral Truvada® plus rectal gel lubricant application daily. This study will entail 4 study visits at the Emory University Hope Clinic. During the first visit (time 0), all men will be screened for eligibility and undergo written informed consent, physical examination, rapid HIV testing, phlebotomy for screening laboratories, and randomization. During study visit 2 prior to the initiation of study product (time 1-6 weeks), participants will undergo phlebotomy, collection of rectal secretions, and rectal biopsy via rigid sigmoidoscopy for establishment of baseline values. During study visit 3 (time 4-16 weeks), men will be dispensed and instructed on the at-home application of rectal lubricant and/or oral Truvada. During study visit 4 (time 5-26 weeks), men will return after 7 consecutive days of study product use for repeat phlebotomy, collection of rectal secretions, and rectal biopsy via rigid sigmoidoscopy. After collection, biologic specimens will be immediately transported by courier to CDC (laboratory of [name]) for processing. Specimens will be processed immediately for *ex vivo* laboratory assays that will include PrEP drug concentrations, inflammatory cytokine levels, HIV target cell measurement and characterization by flow cytometry, and *in vitro* HIV infection assays. Comparison of assay results among the 3 study arms should determine if rectal lubricant usage reduces PrEP drug concentrations, increases inflammation, or increases the proportion or susceptibility of HIV target cells in the rectal mucosa.

Duration: The duration of this study is 2 years. Participants will be considered 'on-study' for no more than 26 weeks.

Sample size: For this protocol we will recruit 90 HIV-negative MSM who meet eligibility criteria outlined in the protocol.

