These studies should provide important laboratory results to help inform policy and public health officials as to usage of hyperosmolar rectal lubricants in concert with oral PrEP. Pharmacological analyses will provide important data as to whether lubricant usage diminishes the ratio of drug to substrate in HIV target cells in the rectum that may reduce PrEP effectiveness. Immunological studies will help us understand whether lubricant usage

9/26/16

TITLE OF PROJECT: PrEP, LUBE, AND THE RECTAL MUCOSA IN MSM AT RISK OF HIV

Emory IRB00077593

PRINCIPAL INVESTIGATOR: [name], MPH

increases inflammation and the concentrations of HIV target cells in the rectum of men taking oral PrEP. The *ex vivo* virus infection assays described here will provide a surrogate measure of whether lubricant usage increases susceptibility to rectal infection with HIV for men taking oral PrEP. Together the combination of these studies should help determine if rectal lubricant usage may abrogate the potential anti-HIV benefits of oral PrEP.

Public Health Relevance: Information about the impact of rectal lubricant use in men who have sex with men will better inform policy makers and the public to make important choices regarding the safety of rectal lubricant usage in the presence of pre-exposure prophylaxis.

Goal: To determine if PrEP efficacy can be abrogated by use of rectal lubricants in MSM.

STUDY POPULATION

A total of 70 HIV-negative MSM aged 18-49 will be recruited from existing Emory University study databases of MSM who have agreed to future contact about research opportunities. We will also recruit men from print and on-line advertisements. Research recruiters at the Hope Clinic and the Rollins School of Public Health are experienced in recruiting this population for research studies, including those with rectal biopsies, and do not anticipate problems. [name] is currently conducting an Emory IRB approved study of the effects of unprotected anal intercourse on the rectal mucosa. This study involves recruiting a similar population to undergo repeated rectal biopsy procedures that are timed with sexual intercourse. We expect approximately 10-15% of men will not complete the study, therefore the sample size of 70 men will likely result in study completion for 60 men.

INCLUSION CRITERIA FOR MSM

- 1) HIV-negative man who reports receptive anal sex with another man in the last 6 months aged 18-49 years

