Men will be asked to abstain from receptive anal intercourse while using PrEP and/or lubricant during the study protocol in order to limit additional exposures (e.g. semen, douching, additional lubricants) to the rectal mucosa. Men taking PrEP will be counseled that they should not expect to achieve protection from HIV infection by taking PrEP during this study as it is a limited, 7-day course. All men included in the study have a interest in taking PrEP for HIV prevention, will be referred to an area PrEP provider at the termination of the study. The Hope Clinic has compiled a resource sheet of area providers that will be distributed to interested participants.

Risks of rectal lubricant application

Personal lubricants are commonly used during sexual intercourse to reduce friction between body parts. Multiple lubricants are available over the counter in local pharmacies. The FDA designates personal lubricants as medical devices, therefore there is no requirement for human safety testing prior to marketing.⁴ There have been a handful of studies that suggest personal lubricants, particularly hyperosmolar lubricants (e.g. Astroglide brand), can damage human tissues and potentially increase susceptibility to HIV or other STDs.^{2,3,5} Clearly, more research is needed into this question of lubricant safety and HIV transmission. This study is designed to answer some of these outstanding questions. To minimize the risk of rectal lubricant application, we will counsel all participants about the possibility of tissue damage with the use of lubricants and recommend use of condoms for all sexual acts to reduce transmission of HIV and other STDs. In addition, we will ask men to abstain from receptive anal intercourse for the one week period when they are using study product and for 1 week after both rectal biopsy procedures (visits 2 and 4).

Rigid sigmoidoscopy and biopsies

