TITLE OF PROJECT: PrEP, LUBE, AND THE RECTAL MUCOSA IN MSM AT RISK OF HIV

Emory IRB00077593

NCT02401230

PRINCIPAL INVESTIGATOR: [name], MPH

19Jan2018

STATISTICAL ANALYSIS PLAN

Drug and dNTP concentrations were normalized to fmol/million cells and fmol/mg rectal tissue in blood and tissue, respectively. Detectable drug and dNTP concentrations as well as immune cell proportions were compared between the Truvada, Rectal Gel Lubricant and Rectal Gel Lubricant + Truvada study arms using a Wilcoxon Rank Sum Test. Left censoring was observed for drug concentration measurements below the limit of detection.

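### The SAP specifies a rank-sum test but no effect estimate or confidence interval, so a non-significant result could not show how large a loss of rectal drug has been ruled out

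*SAP*

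**What the plan says.** The SAP has three sentences. The first gives the normalisation of drug and dNTP concentrations. The second gives the analysis: values that could be detected for drug and dNTP, together with the proportions of immune cells, are compared across the three arms "using a Wilcoxon Rank Sum Test". The third says "Left censoring was observed for drug concentration measurements below the limit of detection" and gives no method for those values. The SAP states no effect measure, interval, significance level or size of loss that would matter, and the protocol has no statistical section.

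The protocol asks a good deal of this comparison. Its opening Design paragraph says "Comparison of assay results among the 3 study arms should determine if rectal lubricant usage reduces PrEP drug concentrations", and goes on to inflammation and HIV target cells. The Goal, in the Project Description, is "To determine if PrEP efficacy can be abrogated by use of rectal lubricants in MSM". The same section says of the laboratory work: "These studies should provide important laboratory results to help inform policy and public health officials".

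**The concern.** Each of these questions has two possible answers: lubricant lowers drug in the rectum, or it does not to any extent that matters. A small p-value can support the first. A large one supports neither, because it arises both when there is no effect and when the study is too imprecise to see one. An interval separates these two cases, and none is specified.

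At stake is what the trial can say if the test is not significant. Without an estimate and interval, neither the investigators nor the policy audience named in the protocol could tell whether a loss of a quarter, a half or more of rectal drug had been excluded.

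**Working it through.** **Inputs from the protocol.** Study Population: 70 men recruited, 10-15% not completing, 60 completers. Sample size paragraph and Project Description: 90 men.

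**The plan's own figure first.** 70 × 0.85 = 59.5 and 70 × 0.90 = 63, so 60 completers is reproduced. With equal allocation, 60 / 3 = 20 per arm. That agrees with the Project Description, where two assays take 10 men each from every arm. From 90 men, 90 / 3 = 30 per arm before any dropout. After 10-15% dropout it would be 76.5 to 81 men in all, about 26 to 27 per arm. The 90 and the 70/60 do not agree, so I carry both. No power or precision figure is stated, so there is none to reproduce.

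**Assumptions (not in the documents).** Equal allocation, two-sided 5% level, log-normal drug levels, SD of ln(concentration) 0.5 to 1.0, and every value detectable.

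**Precision.** The Hodges-Lehmann interval inverts the rank-sum test. Under normality the test's efficiency relative to the t-test is 3/π = 0.955. The approximate half-width of the 95% interval, in SD units, is

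h = t(0.975, 2n − 2) × √(2/n) / √0.955

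- n = 20: 2.024 × 0.3162 / 0.977 = 0.655
- n = 30: 2.002 × 0.2582 / 0.977 = 0.529

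If the observed ratio (Truvada plus gel over Truvada) is exactly 1, the interval is exp(±h × SD). The largest loss still inside it is 1 − exp(−h × SD).

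| n per arm | SD of ln | 95% interval at observed ratio 1 | Loss still inside |
|---|---|---|---|
| 20 | 0.5 | 0.72-1.39 | 28% |
| 20 | 0.75 | 0.61-1.63 | 39% |
| 20 | 1.0 | 0.52-1.93 | 48% |
| 30 | 0.5 | 0.77-1.30 | 23% |
| 30 | 0.75 | 0.67-1.49 | 33% |
| 30 | 1.0 | 0.59-1.70 | 41% |

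A less favourable null leaves more open. If the observed ratio is below 1 and only just non-significant, the lower limit is near exp(−2 × h × SD). At 20 per arm that is 0.52 to 0.27, a loss of 48-73%. At 30 per arm it is 0.59 to 0.35, a loss of 41-65%.

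**Power for a true halving.** Power ≈ Φ( ln 2 / (SD × √(2/(0.955n))) − 1.96 ). At 20 per arm this is 0.99, 0.81 and 0.57 for SD 0.5, 0.75 and 1.0. At 30 per arm it is above 0.99, 0.94 and 0.75. Simulation of the rank-sum test (2,000 runs per setting) gave 0.99, 0.80 and 0.54 at 20 per arm.

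**Simulated nulls.** With no true effect and 20 per arm, the lower limit of the Hodges-Lehmann interval fell below 0.5 in 1%, 20% and 48% of non-significant results for SD 0.5, 0.75 and 1.0.

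**The case against.** The strongest reply is that this is a small laboratory study asking directional harm questions, which a difference test addresses. The SAP does not say that p-values are all that will be reported, and nothing in the documents plans a claim of no effect. All of that is true. The accurate statement is that no estimate or interval is specified. It still stands that the protocol expects the comparison to settle a question to which no is a possible answer.

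A reader might infer more than the documents support, in four ways:

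- **That a non-significant result is likely at these sizes.** This depends on the true effect and the SD. For a true halving, power at 20 per arm is 0.99 at SD 0.5 and still about 0.57 at SD 1.0.
- **That precision for drug levels is that of 10 men per arm.** The Project Description limits 10 per arm to flow cytometry and to the infection assay. Rectal drug is to be measured in biopsies from every man. In the two 10-per-arm assays the feared change is an increase, so a percentage loss does not apply.
- **That policy readers would take a null result as reassurance.** The protocol says the results will inform policy. It does not say how a null result would be read.
- **That the counselling statement, "they should not expect to achieve protection from HIV infection by taking PrEP during this study", shows the endpoints to be invalid.** It is safety advice about a short course. The Project Description already calls the infection assay a surrogate. The efficacy wording of the Goal is a secondary, editorial matter.

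A pre-set margin is also open to argument. The documents give no relation between drug level and protection from which to derive one. The SAP is dated January 2018 and written in the past tense, so data may already have been seen.

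**Conclusion.** The point holds as a cheap improvement to the analysis. The plan specifies a test with no estimate or interval, and a non-significant result from it could not show what loss of rectal drug has been excluded. Under the assumed log SD of 0.5 to 1.0 and equal allocation, even an observed ratio of exactly 1 leaves a 28-48% loss open at 20 per arm and 23-41% at 30 per arm.

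The size rests on that SD. At 0.5, with a ratio near 1, only about a quarter of the drug level is left open, and the documents do not say whether that matters. Actual intervals would be wider than those tabulated if dropout or non-detectable values reduce the numbers compared. The lack of an estimate and interval does not depend on any of these assumptions.

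**What to change.** For Truvada plus gel versus Truvada, for tissue drug level and for the drug:dNTP ratio that the Project Description treats as central:

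1. Report the Hodges-Lehmann shift on the log scale, back-transformed to a ratio, with its 95% confidence interval, beside the rank-sum p-value. The interval comes from inverting the same test, so the two agree.
2. Keep values below the limit of detection in the comparison, for example ranked lowest, and do not restrict it to detectable values. Give the number of such values per arm. If they are so many that the estimate or a limit falls on a censored difference, say so and report a bound.
3. Word any null result by the losses that the interval excludes, on the laboratory surrogates measured after 7 days of product, and not as showing that efficacy is not abrogated.
4. Label any margin for an unimportant loss as post hoc if it is set after data were seen.

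The cost is a few sentences in the SAP and one extra line of output per comparison. No further participants or assays are needed. The downside is that a null result supports a weaker claim.

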To address the impact of a popular, over the counter, gel lubricant use in the rectum in MSM on PrEP, investigators at Emory University will collaborate with [name] at the CDC to recruit and randomize 90 MSM into a three-arm study of PrEP and lubricants: (1) daily oral Truvada® for 7 days, (2) daily gel lubricant applied rectally for 7 days or (3) oral Truvada® plus rectal gel lubricant application daily for 7 days. At CDC, *ex vivo* laboratory assays will be used to evaluate the impact of rectal lubricant use on oral PrEP's effectiveness. Blood, rectal secretions and rectal biopsies obtained by rigid sigmoidoscopy (at approximately 8 -10 cm from the anal verge) will be collected from men in all three study arms at least 21 days prior to initiation of treatment and immediately following 7 days of consecutive use of assigned product. Specimens will be processed immediately for *ex vivo* laboratory assays at CDC. Blood plasma and PBMCs will be used to measure extracellular and intracellular drug concentrations as well as intracellular concentrations of the natural dNTP substrates to assess adherence to oral Truvada® and to compare changes in the ratio of drug to natural substrate in peripheral blood. Rectal secretions from all participants will be analyzed to measure changes in soluble immunological cytokines in the presence of gel lubricant usage that may indicate associated increases in inflammation. Rectal lymphocytes will be isolated from the rectal biopsies collected from each man and analyzed for concentrations of intracellular tenofovir and emtricitabine as well as natural substrates, dATP and dCTP, to evaluate the potential for gel lubricant to alter the ratio of antiretroviral drug to natural substrate in the rectal mucosa. Additionally, rectal lymphocytes from 10 participants in each arm will be characterized using multicolor flow cytometry to observe potential changes in the proportion and activation state of HIV target cells within the rectal mucosa. Rectal lymphocytes from the remaining 10 participants in each arm will be subjected to *in vitro* infection with HIV to test for changes in the susceptibility to virus infection in the presence of gel lubricant usage.

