During the screening visit, eligible MSM will provide written informed consent after all their questions are answered in a private exam room at the Hope Clinic. Subjects will also receive an approved HIPAA statement and will be informed about the way their protected health information will be used and stored. Copies of the consent/HIPAA form for this project will not be placed in individuals' medical records since this study collects sensitive information such as HIV status and sexual orientation.

After provision of informed consent, a medical history and physical examination will be conducted by the PI to evaluate for exclusion criteria. A rapid HIV test with finger stick whole blood (OraQuick or INSTI) will be performed by the PI or study coordinator who will be certified in HIV counseling and testing to confirm eligibility. Peripheral blood will be drawn for a complete blood count and coagulation tests. Finally, MSM will be randomized to one of three study arms:

Arm 1. Use of rectal gel lubricant alone for 7 days prior to study visit 4.

Arm 2. Use of PrEP alone for 7 days prior to study visit 4

Arm 3. Use of both rectal gel lubricant and PreP for 7 days prior to study visit 4.

TITLE OF PROJECT: PrEP, LUBE, AND THE RECTAL MUCOSA IN MSM AT RISK OF HIV
Emory IRB00077593
PRINCIPAL INVESTIGATOR: [name], MPH

This study will not be blinded, so both investigator and participant will be aware of randomization assignment. Participants will be asked to abstain from receptive anal intercourse for at least 3 days prior to study visit 2.

Visit 2:

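### The SAP appears to have been written with assay data in hand, so its below-limit handling, tissue unit and test are not shown to be pre-specified

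*SAP*

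**What the plan says.** The SAP is a single paragraph dated 19Jan2018. It covers units ("Drug and dNTP concentrations were normalized to fmol/million cells and fmol/mg rectal tissue in blood and tissue, respectively"), outcomes and arms ("Detectable drug and dNTP concentrations as well as immune cell proportions were compared between the Truvada, Rectal Gel Lubricant" and the combined arm), the method ("using a Wilcoxon Rank Sum Test"), and values below the limit ("Left censoring was observed for drug concentration measurements below the limit of detection"). It states no significance level and no p-value.

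The protocol supplied carries the page footer 9/26/16. It has no statistical section: no primary endpoint, test, error rate or rule for values below the limit. Its Design paragraph says "Comparison of assay results among the 3 study arms should determine if rectal lubricant usage reduces PrEP drug concentrations". Its Project Description lists the planned assays; rectal lymphocytes isolated from the biopsies are to be "analyzed for concentrations of intracellular tenofovir and emtricitabine as well as natural substrates, dATP and dCTP". Under Visit 1 it states "This study will not be blinded, so both investigator and participant will be aware of randomization assignment".

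**The concern.** A plan says how values below the limit will be treated. This one says that such values occurred, which is normally known only once assay results exist. With every other verb also in the past tense, the text reads as an account of work done. Nothing earlier in the supplied documents fills the gap.

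The choice of handling can matter for the main question. If lubricant lowered drug levels, some men in the combined arm could fall below the limit. A test on detectable values drops exactly those men, whereas a test that ranks them lowest keeps them. If the choice was made with results in view, the nominal error rate of even one comparison is no longer assured. A reader of a file titled as an analysis plan may not realise this.

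**Working it through.** **1. Dates.** The protocol footer is 26 September 2016 and the SAP is dated 19 January 2018, just under 16 months later. The protocol says "The duration of this study is 2 years". No first-visit, last-visit, data-lock or first-analysis date is given, so the order of SAP and data has to be inferred from wording.

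**2. What was fixed beforehand.** The two documents side by side:

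| Item | Protocol (9/26/16) | SAP (19Jan2018) | Shown to be pre-specified? |
|---|---|---|---|
| Drug and dNTP levels | Named in Project Description | Compared | Yes, as outcomes |
| HIV target-cell proportions | Named in Project Description | Immune cell proportions compared | Yes, as a broad outcome |
| Tissue measure | Intracellular, in isolated rectal lymphocytes | fmol per mg of tissue | No |
| Detectable values only | Not mentioned | Stated | No |
| Values below the limit | Not mentioned | Censoring reported, handling unclear | No |
| Test | Not mentioned | Wilcoxon rank sum | No |
| Drug-to-substrate ratio | Named in Project Description | Absent | Dropped without comment |
| Cytokines in secretions | Named in Project Description | Absent | Dropped without comment |
| In vitro HIV infection | Named in Project Description | Absent | Dropped without comment |

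**3. Size, as an illustration.** The SAP has no figure of its own to reproduce here.

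- *Arm size.* Study Population expects 60 completers from 70 recruited at 10 to 15% loss. 70 × 0.85 = 59.5 agrees with that, while 70 × 0.90 = 63 is a little higher. 60 / 3 = 20 per arm. The Design paragraph gives 90 men, and 90 / 3 = 30 per arm before loss.
- *Assumed, not in the documents.* Two-sided level 0.05; log-normal drug values with the same distribution in both arms; 10, 20 or 30% below the limit.
- *Two handlings.* (a) Rank-sum on detectable values only. (b) Rank-sum on all men, with values below the limit tied lowest. A false positive is counted when the smaller p-value is under 0.05.
- *Bounds.* If the two tests always agreed, the rate would be 5%. If they never rejected together, it would be 2 × 5% = 10%.

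Results from 6,000 simulated trials per setting:

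| Below limit | 20 per arm | 30 per arm |
|---|---|---|
| 10% | 7.3% | 6.9% |
| 20% | 8.2% | 8.0% |
| 30% | 7.9% | 8.4% |

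A further set of 3,000 trials per setting gave 6.3 to 8.7%. At a rate of 8% the simulation standard error is √(0.08 × 0.92 / 6,000) = 0.35 percentage points, or 0.5 points with 3,000 trials, so the two sets agree. Each analysis taken alone stayed near its nominal level, at 3.8 to 5.5%. The inflation comes from the choice and not from either test.

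**The case against.** The strongest reply is that the order of events is not documented. The date belongs to this file. It does not show when the methods were chosen, and the text may condense an earlier plan that was not supplied. That stands, and is why the point says only that the SAP appears to have followed the data.

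Four stronger readings are tempting, and the documents do not support them:

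- *That the outcomes are post hoc.* Every broad outcome in the SAP is named in the Project Description. What remains is narrower: handling, unit, test, and the three outcomes left out.
- *That open label means arm-level results were visible while choices were open.* The statement under Visit 1 concerns investigator and participant. Specimens went to CDC under codes that the laboratories could not link to participants (Visit 2, Visit 4, Breach of Confidentiality). The documents do not say when assay results were joined to arm.
- *That a confirmatory claim is undermined.* The protocol makes none. The Design sentence is strongly worded, but the Project Description closes by saying the studies should help to settle the question, and it calls the infection assays a surrogate.
- *That reported p-values are wrong.* The SAP gives none, and the 5% level is assumed here.

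It is also fair to say that the simulated rates assume the smaller p-value is always taken. They show what an open choice permits, not what was done.

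**Conclusion.** The point holds in limited form. The past tense and the report of observed censoring strongly suggest that the SAP was written once assay data existed. No supplied document shows that the detectable-only restriction, the treatment of values below the limit, the tissue unit or the rank-sum test came earlier. Three protocol outcomes disappear without explanation.

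For one drug comparison, the possible cost is a false-positive rate of roughly 6 to 9% in place of about 5%. That rests on the assumed level, arm sizes and share below the limit, and on free choice between two handlings. It is modest, and it is not evidence of selection. The practical consequence is that these tests should not be presented as pre-planned unless an earlier plan can be cited.

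**What to change.** 1. For the comparison of the two Truvada-containing arms, report each drug outcome twice: on detectable values only, and on all men with values below the limit ranked lowest. Say whether the conclusion depends on the choice.
2. Cite a dated earlier analysis plan if one exists. If not, state in the SAP that it followed data review, label its tests exploratory, and word conclusions as hypothesis-generating in place of the Design paragraph's language.
3. Report the drug-to-substrate ratio, cytokine and in vitro infection results, or state that they were not analysed.

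The below-limit comparisons use existing data. The cost is a few re-runs, some rewording, and a weaker stated strength of evidence.
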